7.3. Body Weight and Vital Signs

Descriptive statistics will be provided by treatment group for body weight and vital signs as follows:

- Baseline value
- Values at each postbaseline analysis visit
- Change from baseline at each postbaseline analysis visit

A baseline value will be defined as the last available value collected on or prior to the date/time of first dose of study drug. Change from baseline to a postbaseline visit will be defined as the postbaseline value minus the baseline value. Body weight and vital signs measured at unscheduled visits will be included for the baseline value selection. It should be noted that temperature will not be summarized due to different methods of measuring temperature. Oxygen saturation (SpO₂ and PaO₂) will also not be summarized due to collection under different oxygen support statuses.

In the case of multiple values in an analysis window, data will be selected for analysis as described in Section 3.8.2. No formal statistical testing is planned.

A by-participant listing of vital signs will be provided by subject ID number and analysis visit in chronological order. Body weight, height, and BMI will be included in the vital signs listing, if space permits. If not, they will be provided separately.

7.4. Prior and Concomitant Medications

Medications collected at screening and during the study will be coded using the current version of the Gilead-modified World Health Organization (WHO) Drug dictionary.

7.4.1. **Prior Medications**

Prior medications are defined as any medications taken before a participant took the first dose of study drug.

A summary of prior medications will not be provided.

7.4.2. Concomitant Medications

Concomitant medications are defined as medications taken while a participant took study drug. Use of concomitant medications will be summarized by preferred name using the number and percentage of participants for each cohort. A participant reporting the same medication more than once will be counted only once when calculating the number and percentage of participants who received that medication. The summary will be ordered by preferred term in descending overall frequency. For drugs with the same frequency, sorting will be done alphabetically.

For the purposes of analysis, any medications with a start date prior to or on the first dosing date of study drug and continued to be taken after the first dosing date, or started after the first dosing date but prior to or on the last dosing date of study drug will be considered concomitant medications. Medications started and stopped on the same day as the first dosing date or the last dosing date of study drug will also be considered concomitant. Medications with a stop date prior to the date of first dosing date of study drug or a start date after the last dosing date of study drug will be excluded from the concomitant medication summary. If a partial stop date is entered, any medication with the month and year (if day is missing) or year (if day and month are missing) prior to the date of first study drug administration will be excluded from the concomitant medication summary. If a partial start date is entered, any medication with the month and year (if day is missing) or year (if day and month are missing) after the study drug stop date will be excluded from the concomitant medication summary. Medications with completely missing start and stop dates will be included in the concomitant medication summary, unless otherwise specified. Summaries will be based on the Safety Analysis Set. No formal statistical testing is planned. All prior and concomitant medications (other than per-protocol study drugs) will be provided in a by-participant listing sorted by subject ID number and administration date in chronological order.

7.4.3. COVID-19 Medications Other Than the Study Drug

COVID-19 medications from the first day of first dose of study drug administration until the end of the study will be categorized into the following categories:

- Experimental antiviral
- Immune modulator
- Anti-inflammatory
- Antiviral antibody therapy
- Other medication

Refer to Table 13-1 for the list of COVID-19 medications and the associated categories. It should be noted that a COVID-19 medication may belong to more than one category.

One of the secondary endpoints is the proportion of participants with concomitant use of medications other than RDV for treatment of COVID-19. Therefore, a summary table will present the number and percentages of participants with concomitant use of COVID-19 medications by cohort and overall for the Safety Analysis Set, sorted first by categories and then by PT in descending order of total frequency.

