1.1. Study Objectives

The primary objective of this study is as follows:

- To evaluate the safety and tolerability of remdesivir (RDV; GS-5734TM) in participants with laboratory-confirmed COVID-19 aged 0 days to < 18 years
- To evaluate the pharmacokinetics (PK) of RDV in participants with laboratory-confirmed COVID-19 aged 0 days to < 18 years

The secondary objectives of this study are as follows:

- To evaluate the efficacy of RDV in participants with laboratory-confirmed COVID-19 aged 0 days to < 18 years
- To determine the antiviral activity of RDV in participants with laboratory-confirmed COVID-19 aged 0 days to < 18 years
- To evaluate the change from baseline in oxygenation use
- To evaluate the change from baseline in the use of mechanical ventilation or extracorporeal membrane oxygenation (ECMO)
- To evaluate clinical improvement using the Pediatric Early Warning Score (PEWS) scale in participants with laboratory-confirmed COVID-19 aged 0 days to < 18 years
- To determine sulfobutylether β-cyclodextrin sodium (SBECD) exposures (where possible)
- To provide data on use of medications other than RDV for treatment of COVID-19

The exploratory objectives of this study are as follows:

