Appendix 2. Pediatric Early Warning Score

Appendix 3. Programming Specifications

1) If the age from the Day 1 eCRF is not available, age will be calculated as follows:

Only year is provided for the date of birth (DOB). Use July 1 for the month and day.

- a) AGE (years) is calculated from the number of days between the DOB and Study Day 1,
- b) Use the SAS INTCK function to determine the number of "1st-of-month days" (eg, January 1st, February 1st, March 1st) between DOB and Day 1 (inclusive),
- c) Divide the result in (b) by 12, AGE = the integer of the result in (c), Age for laboratory test reference range will be based on the age at the sample collection date.
- 2) All screened participants refer to all participants who are screened (ie, with non-missing screening date) and have a screening number. For summaries the same participant is counted only once.
- 3) Screen failure participants are the participants who were screened and answered "No" for any inclusion criteria or "Yes" for any exclusion criteria regardless of which version of protocol the participant was consented to.
- 4) Participants in the All Enrolled Analysis Set are defined as participants enrolled into the study. IXRSRAND is the source to determine whether the participants is enrolled (ie, participant with non-missing ENRDTN in the IXRSRAND dataset), and confirmed by the eCRF ENROLL dataset (ie, ENROLLYN = "Yes" in ENROLL dataset).
- 5) Enrolled treatment (ie, TRT01P in ADSL) is derived from IXRSRAND, while actual treatment received (ie, TRT01A in ADSL) is assigned as the enrolled treatment if the participant took at least 1 dose of study drug and assigned as blank if the participant was never dosed.
- 6) In the disposition table, the reasons for premature discontinuation are displayed in the order as they appear on the eCRF.
- 7) Body mass index (BMI)

BMI will be calculated only at baseline as follows:

- BMI = (weight [kg]) / (height [meters]²)

Baseline height and weight will be used for this calculation if available.

8) Details of additional COVID-19 medications are provided in table below.

Drug name	ATC Code	WHODRUG Preferred Term
Chloroquine	P01BA	CHLOROQUINE
Hydroxychloroquine	P01BA	HYDROXYCHLOROQUINE
Lopinavir/ritonavir	J05AR	LOPINAVIR/RITONAVIR
Ribavirin	J05AP	RIBAVIRIN
Bamlanivimab/Etesevimab		BAMLANIVIMAB/ETESEVIMAB
Casirivimab/Imdevimab		CASIRIVIMAB/IMDEVIMAB
Molnupiravir		MOLNUPIRAVIR

Table 13-1.Additional COVID-19 Medications

ATC = anatomical therapeutic chemical

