Additional medications may be included during final review of concomitant medications prior to data finalization.

9)	Grouping on	COVID-19	medications	other than	the study drug
- /					

Table 13-2.Grouping on the COVID-19 Medications other than the Study Drug

Standardized Medication Name	Experimental antiviral	Immune modulator	Anti- inflammatory	AntiViral antibody therapy	Other medication
ANAKINRA	N	Y	Y	N	Ν
AZITHROMYCIN	Y	Y	Y	N	Ν
BETAMETHASONE	N	Y	Y	N	Ν
CLARITHROMYCIN	N	N	Y	N	N
CYCLOBENZAPRINE	N	Ν	N	N	Y
DEXAMETHASONE	N	Y	Y	N	Ν
DEXAMETHASONE SODIUM PHOSPHATE	N	Y	Y	N	N
DIPHENHYDRAMINE; ZINC ACETATE	N	Ν	N	N	Y
ENOXAPARIN	N	N	N	N	Y
ENOXAPARIN SODIUM	N	N	N	N	Y
GANCICLOVIR	Y	N	N	N	N
HYDROCORTISONE	N	Y	Y	N	Ν
HYDROCORTISONE SODIUM SUCCINATE	N	Y	Y	N	N

Standardized Medication Name	Experimental antiviral	Immune modulator	Anti- inflammatory	AntiViral antibody therapy	Other medication
HYDROXYCHLOROQUIN E	Y	Ν	Ν	N	Ν
IMMUNOGLOBULIN G HUMAN	N	Y	N	N	N
IMMUNOGLOBULIN HUMAN NORMAL	N	Y	N	N	Ν
IMMUNOGLOBULINS NOS	N	Y	N	Ν	Ν
LEVOFLOXACIN	N	Ν	Ν	Ν	Y
METHYLPREDNISOLONE	N	Y	Y	Ν	Ν
ONDANSETRON	N	N	N	N	Y
PLASMA	N	Ν	N	Y	Ν
POTASSIUM PHOSPHATE DIBASIC	Y	Y	Y	N	N
POTASSIUM PHOSPHATE DIBASIC;SODIUM PHOSPHATE	Y	Y	Y	Ν	Ν
PREDNISOLONE	N	Y	Y	N	Ν
PREDNISOLONE SODIUM PHOSPHATE	N	Y	Y	N	N
PREDNISONE	N	Y	Y	N	N
REMDESIVIR	N	N	N	N	Y
RITUXIMAB	N	Y	N	Ν	N
TOCILIZUMAB	N	Y	Y	N	N
ZINC	N	Ν	N	N	Y

Additional medications may be included during final review of COVID-19 medications other than the study drug prior to data finalization.

- 10) Graded Laboratory Abnormalities Summary
 - The following labels will be used for laboratory abnormalities and Grade 3 or 4 laboratory abnormalities summary tables and listings:

Battery	Lab Test Label Used in l-labtox Listing	Toxicity Direction	Lab Test Label Used in t-labtox Table
Hematology	Basophils	Increase	Basophils (Increased)
	Eosinophils	Increase	Eosinophils (Increased)
	Hemoglobin	Decrease	Hemoglobin (Decreased)
	Lymphocytes	Decrease	Lymphocytes (Decreased)
	Monocytes	Increase	Monocytes (Increased)
	Neutrophils	Decrease	Neutrophils (Decreased)
	Platelets	Decrease	Platelets (Decreased)
	WBC	Decrease	WBC (Decreased)
Chemistry	Albumin	Decrease	Albumin (Decreased)
	Alkaline Phosphatase	Increase	Alkaline Phosphatase (Increased)
	ALT	Increase	ALT (Increased)
	AST	Increase	AST (Increased)
	Calcium	Decrease	Calcium (Decreased)
	Calcium, Ionized	Decrease	Calcium, Ionized (Decreased)
	Creatine Kinase	Increase	Creatine Kinase (Increased)

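### Table 13-2 counts remdesivir as an 'Other medication', although the secondary endpoint it feeds covers medications other than RDV (and Section 7.4.3 cites the wrong table)

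*SAP*

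**What the plan says.** The secondary objective in SAP Section 1.1 is "To provide data on use of medications other than RDV for treatment of COVID-19". Section 7.4.3 turns this into an endpoint: "One of the secondary endpoints is the proportion of participants with concomitant use of medications other than RDV for treatment of COVID-19". The result is a table of numbers and percentages by cohort and overall in the Safety Analysis Set, sorted by category and then by preferred term. The five categories are experimental antiviral, immune modulator, anti-inflammatory, antiviral antibody therapy and other medication.

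For the drug list and its categories the section says "Refer to Table 13-1 for the list of COVID-19 medications and the associated categories". Table 13-1 in Appendix 3 has the columns "Drug name ATC Code WHODRUG Preferred Term" and seven drugs. The next table, 13-2, is titled "Grouping on the COVID-19 Medications other than the Study Drug". It gives 30 names with a Y or N in each of the five categories. Its REMDESIVIR row has N in the first four and Y under Other medication.

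Section 7.4.3 sets its own period: "COVID-19 medications from the first day of first dose of study drug administration until the end of the study will be categorized". Section 7.4.2, on concomitant medications in general, says that a drug with "a start date after the last dosing date of study drug will be excluded from the concomitant medication summary".

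**The concern.** The endpoint and the objective both exclude RDV by name, yet the only table that can be used to build the summary includes it. A programmer who follows the table would count a non-study RDV record as use of a medication other than RDV. The reported proportion would then no longer measure what the endpoint describes.

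The wrong table number makes this easier to miss. The table that Section 7.4.3 names does not contain the RDV row, so someone checking the section against its cited source would not come across it.

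At stake is the accuracy of a reported percentage for a stated secondary endpoint. No hypothesis test, power statement or error rate depends on it.

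**Working it through.** The plan states no figure to reproduce. The check compares the endpoint with the tables and then does simple arithmetic.

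**1. Which table can produce the summary?**
- Table 13-1: 7 drugs and 0 of the 5 categories. Its other use is in Section 3.7, as the list that triggers exclusion of viral load samples.
- Table 13-2: 30 names and all 5 categories. Its title repeats the heading of Section 7.4.3.

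Only Table 13-2 can supply the five-category summary, so the citation should read 13-2.

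**2. What does Table 13-2 do with RDV?** Eight names carry a Y under Other medication: cyclobenzaprine, diphenhydramine with zinc acetate, enoxaparin, enoxaparin sodium, levofloxacin, ondansetron, remdesivir and zinc. REMDESIVIR is 1 of these 8 and has no other category.

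**3. Does any text remove it?**
- Section 7.4.3: no exclusion rule.
- Appendix 3, at Table 13-2: no footnote or exception, only a note that medications may be added.
- Section 7.4.2: "All prior and concomitant medications (other than per-protocol study drugs) will be provided in a by-participant listing". The parenthesis governs the listing, not the Section 7.4.3 summary. It also removes only study drug, so non-study RDV would stay in.

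**4. Which records are caught?** Non-study RDV taken between the first study dose and the end of the study. The SAP does foresee non-study RDV, since Section 3.7 has a viral load rule for participants who received IV RDV before enrollment. RDV stopped before the first study dose falls outside the Section 7.4.3 period and is not counted.

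**5. How far can one participant move the result?** Let *n* be the number in the Safety Analysis Set for the column.
- REMDESIVIR preferred-term line: rises by 1/*n* in every case.
- Other medication total: rises by 1/*n* if RDV is the participant's only drug in that category.
- Any-use proportion: rises by 1/*n* only if RDV is the only listed drug the participant took.

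The planned numbers are in Sections 1.2 and 1.3: 12 in each of Cohorts 1 to 4, and at least 52 in total. If all enrolled participants are treated:
- one cohort: 1/12 = 0.083, or 8.3 percentage points;
- overall: at most 1/52 = 0.019, or 1.9 percentage points.

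**The case against.** The strongest reply is that the row is deliberate. The section heading and the title of Table 13-2 both speak of medications other than the study drug, and commercially supplied remdesivir is arguably not the study drug. That explains why the row exists. It does not settle the conflict, because non-study RDV is still RDV, and the endpoint and the objective exclude RDV, not only study drug.

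A second reply is that the summary is broken down by preferred term, so a REMDESIVIR line would be visible. This is true and helps a careful reader, but it does not correct the category total or the any-use proportion.

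A third is that medications may be added to both tables before data finalization. Additions neither correct a citation nor remove a row. They do allow a category to be given to any Table 13-1 drug that was actually taken.

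Some stronger readings are tempting, and the document does not support them:
- A reader might infer that the wrong citation would cut the endpoint down to the seven drugs of Table 13-1. A five-category summary cannot be built from a table without categories, and only one table fits. The slip is close to clerical.
- A reader might infer that Sections 7.4.2 and 7.4.3 contradict each other on the period. Section 7.4.3 states its own, and the Section 7.4.2 exclusion is written for a different summary. Only the word 'concomitant' in the endpoint leaves some doubt.
- A reader might infer that the two drug lists ought to match. They serve different purposes, viral load exclusion and descriptive grouping, and nothing in the SAP requires them to agree.

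**Conclusion.** The point holds as a minor inconsistency. As written, the SAP counts REMDESIVIR towards an endpoint defined as medications other than RDV, and it cites the wrong table for the categories.

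The numerical effect is conditional. It arises only if a participant has non-study RDV recorded in the counted period, and the SAP does not say whether any has. The 8.3 and 1.9 points are therefore illustrations per affected participant and not estimates of bias. They rest on the planned numbers and on RDV being the only drug counted for that participant in the proportion concerned. It would go too far to say that the endpoint will be misreported: with no such participant, the results are unchanged.

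**What to change.** In Section 7.4.3:
- Cite Table 13-2 instead of Table 13-1.
- State that REMDESIVIR is counted neither in the proportion using medications other than RDV nor in the Other medication total, and that any non-study RDV is reported on a separate line or in a footnote.
- Optionally, say that concomitant use in this endpoint follows the section's own period, from first dose to end of study.

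The cost is one corrected table number and one or two sentences. No new data are needed, and the by-participant medication listing already keeps non-study RDV visible. If the SAP is not reopened, the change can be documented in the CSR, as Section 1 provides.

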7.5. Electrocardiogram Results

A by-participant listing of ECG results will be provided by subject ID number (in ascending order).

7.6. Other Safety Measures

A by-participant listing will be provided for those participants experiencing pregnancy during the study.

A by-participant listing of chest imaging reslts will also be provided by subject ID number (in ascending order).

7.7. Changes From Protocol-Specified Safety Analyses

There are no deviations from the protocol-specified safety analyses.

8. PHARMACOKINETIC (PK) ANALYSES

8.1. PK Sample Collection

Sparse PK assessments will be conducted in all participants at participating sites. A single PK blood sample is planned to be collected at the following times and visits:

- Cohorts 1-4 and Cohort 8:
 - Day 2: end of infusion (± 15 minutes) and 4 hours (±30 minutes) post end of infusion
 - Day 3: pre-infusion (≤ 60 minutes) and 2 hours (± 15 minutes) post end of infusion

-CCI

- Cohorts 5, 6 and 7, Day 2 OR Day 3:
 - Day 2: end of infusion (± 15 minutes) and 4 hours (±30 minutes) post end of infusion
 - Day 3: pre-infusion (≤ 60 minutes) and 2 hours (± 15 minutes) post end of infusion

As many of the specified PK time points should be obtained from each participant as is feasible.

8.2. PK Analyses

Concentrations of RDV, the metabolites (GS-441524 and GS-704277), and SBECD in plasma will be determined using validated bioanalytical assays.

The analytes and parameters presented in Table 8-1 will be used to evaluate the PK objectives of the study.

Analytes	Sample Matrix	Parameters
RDV	Plasma	$\begin{array}{c} AUC_{0\text{-}24} \text{ loading dose (h*ng/mL), } C_{max} \text{ loading dose (ng/mL), } AUC_{tau} \\ \text{steady state (h*ng/mL), } C_{max} \text{ steady state (ng/mL), } t_{1/2} \text{ steady state (h), } CL_{ss} \\ (L/h), \ V_{ss}(L) \end{array}$
GS-441524	Plasma	AUC ₀₋₂₄ loading dose (h*ng/mL), C _{max} loading dose (ng/mL), AUC _{tau} steady state (h*ng/mL), C _{max} steady state (ng/mL), C _{tau} steady state (ng/mL), t _{1/2} steady state (h)
GS-704277	Plasma	AUC ₀₋₂₄ loading dose (h*ng/mL), C_{max} loading dose (ng/mL), AUC _{tau} steady state (h*ng/mL), C_{max} steady state (ng/mL), $t_{1/2}$ steady state (h)

Table 8-1.PK Parameters for Each Analyte

8.2.1. Statistical Analysis Methods

Individual participant concentration data for RDV, the metabolites (GS-441524 and GS-704277), and SBECD will be listed and summarized using descriptive statistics. Summary statistics (n, mean, SD, coefficient of variation [%CV], median, min, max, Q1, and Q3) will be presented by time point. In addition, the geometric mean, 95% CI of the geometric mean, and the mean and SD of the natural log-transformed values will be presented for individual participant PK parameter data.

Individual concentration data listings and summaries will include all participants with concentration data. The sample size for each time point will be based on the number of participants with nonmissing concentration data at that time point. The number of participants with concentration below the limit of quantitation (BLQ) will be presented for each time point. For summary statistics, BLQ values will be treated as 0 at predose and one-half of the lower LOQ for postdose time points.

The following tables will be provided for each analyte by cohort and overall total:

- Individual participant concentration data and summary statistics
- Individual participant PK parameters and summary statistics

The following figures will be provided for each analyte by cohort and overall total:

- Boxplots of selected PK parameters
 - RDV: AUC_{tau} steady state (h*ng/mL), C_{max} steady state (ng/mL), t_{1/2} steady state (h), CL_{ss} (L/h), V_{ss} (L)
 - GS-441524: AUC_{tau} steady state (h*ng/mL), C_{max} steady state (ng/mL), C_{tau} steady state (ng/mL), t_{1/2} steady state (h)
 - --- GS-704277: AUC_{tau} steady state (h*ng/mL), C_{max} steady state (ng/mL), $t_{1/2}$ steady state (h)
- PK sampling details by participant, including procedures, differences in scheduled and actual draw times, and sample age will be provided in listings.

9. **REFERENCES**

- GS-US-399-5505 Final Clinical Study Report. A Phase 1, Blinded, Randomized, Placebo-Controlled, Multiple-Dose Study Evaluating the Safety, Tolerability, and Pharmacokinetics of Intravenous Remdesivir in Healthy Volunteers. 09 April 2020. Page 63 – 69.
- GS-US-540-5823 Data Monitoring Committee (DMC) Charter. A Phase 2/3 Single-Arm, Open-Label Study to Evaluate the Safety, Tolerability, Efficacy, and Pharmacokinetics of Remdesivir (GS 5734TM) in Participants from Birth to < 18 Years of Age with COVID-19. 22 June 2020. Page 1 – 35.

10. SOFTWARE

SAS® Software Version 9.4. SAS Institute Inc., Cary, NC, USA.

nQuery Advisor(R) Version 8.5. Statistical Solutions, Cork, Ireland.

11. SAP REVISION

Revision Date (DD MMM YYYY)	Section	Summary of Revision	Reason for Revision

12. APPENDICES

Appendix 1.Study Procedures Table

					Adı	ninistratio	n Period ^ь					Follow-up Period
	Screening	Baseline/ Day 1ª	Day 2	Day 3	Day 4	Day 5	Day 6	Day 7	Day 8	Day 9	Day 10	Day 30 (± 5 days)
Assent/Parent or Legal Guardian consent	Х											
Inclusion/Exclusion criteria	Х											
Focused medical history	Х											
Documentation of SARS-CoV-2 confirmation by PCR	Х											
ECG	Х											
Complete or symptom-directed physical examination	Х	X	X	X	X	Х	Х	X	Х	Х	Х	X
Body weight ^c	Х	Х	X	Х	X	Х	Х	X	Х	Х	Х	X
Height/Length	Х											Xd
Head circumference and last recorded Apgar score if < 24 hours of age	Х											X ^d
Birth weight and gestational age if < 56 days	х											
Vital signs (heart rate, temperature, blood pressure [MAP if available, systolic and diastolic], respiratory rate, oxygen saturation)	Х	Х	x	X	х	Х	X	x	Х	Х	х	X
Documented respiratory status	Х	X	X	X	X	Х	Х	X	Х	Х	Х	X

			Administration Period ^b							Follow-up Period		
	Screening	Baseline/ Day 1ª	Day 2	Day 3	Day 4	Day 5	Day 6	Day 7	Day 8	Day 9	Day 10	Day 30 (± 5 days)
If available, record chest radiographic impression (or other imaging) but not mandatory to perform otherwise	Х	Х	х	Х	Х	Х	Х	x	Х	х	х	
Tanner Stage assessment if ≥ 6 years of age		Х										
Hematology, chemistry, urinalysis	Х		X			Х			Х		Х	Xe
Routine coagulation test (Days 5 and 10 only for Cohorts 5-6 and Day 10 only for Cohort 7)	Х		X			Х			Х		Х	
Inflammatory Markers (D-dimer, Ferritin, qCRP, Procalcitonin, and IL-6)	Х		X			Х			Х		Х	
ESR If ≥4 kg (Cohorts 1-4 only)	Х		X			Х			Х		Х	
Neonatal bilirubin panel for all neonates < 14 days, and any neonate presenting with jaundice	Х										Х	
Serology for SARS-CoV-2 if $\geq 12 \text{ kg} (\text{IgG, IgM, and IgA})^{f}$	X					Х					X	X
Pregnancy test (urine/blood)	Х											

			Administration Period ^b							Follow-up Period		
	Screening	Baseline/ Day 1ª	Day 2	Day 3	Day 4	Day 5	Day 6	Day 7	Day 8	Day 9	Day 10	Day 30 (± 5 days)
Nasopharyngeal and oropharyngeal samples (combined), rectal or fecal swab, and ET aspirates (if intubated) for SARS-CoV-2 PCR testing and possible viral sequencing ^f		Х		X		Х		X			Х	
Pediatric Early Warning Score Improvement Scale ^g	Х	Х	X	X	Х	Х	Х	X	Х	Х	Х	
Ordinal Scale	Х	X	X	X	X	Х	X	X	Х	X	X	
Plasma PK assessmentsh			X	X		X						
IV RDV administration		Xi	Xj	Xj	Xj	Xj	Xj	Xj	Xj	Xj	Xj	
Concomitant medications	Х	X	X	X	X	Х	X	X	Х	X	X	X
Adverse events ^k	Х	X	X	X	X	Х	X	X	Х	X	X	X

CCI

CoV = coronavirus; CRP = C-reactive protein; ECG = electrocardiogram; ET = endotracheal tube; Ig = immunoglobulin; IV = intravenous; MAP = mean arterial pressure; PK = pharmacokinetic; RDV = remdesivir (GS-5734TM); SARS = severe acute respiratory syndrome; TBD = to be determined

a If the Screening and Day 1 visits occur within 24 hours, only the following procedures need to be completed: Tanner Stage assessment and samples for SARS-CoV-2 PCR testing and viral sequencing

- b The following evaluations are to be completed on Days 2-10 or until discharge, whichever comes earlier.
- c CCI

d Record length and head circumference if < 28 days at enrollment.

e Comprehensive metabolic panel (Chemistry 14) only.

f If the subject is discharged prior to Day 10, the Serology for SARS-CoV-2 and SARS-CoV-2 samples/swabs will be collected on the day of discharge. Thereafter, these samples can be collected by assigned study staff at the subject's home or as an outpatient on the assigned days noted above.

g If a subject is on a ventilator, a score of 3 should be given in the respiratory category.

h CCI

i IV administration on Day 1 with either IV RDV 200 mg (Cohort 1), IV RDV 5 mg/kg (Cohorts 2-5), or RDV dose TBD (Cohorts 6-7).

j IV administration daily up to Day 10 with either IV RDV 100 mg (Cohort 1), IV RDV 2.5 mg/kg (Cohorts 2-5), or RDV dose TBD (Cohorts 6-7).

k All subjects presenting with multisystem inflammatory syndrome in children (MIS-C; https://emergency.cdc.gov/han/2020/han00432.asp) should be monitored and treated as clinically indicated.

CCI 1

Version 1.0

	0	1	2	3
Behavior	Playing Appropriate	Sleeping	Irritable	Lethargic and/or Confused and/or Reduced response to pain
Cardiovascular	Within normal parameters for age Pink and/or Capillary refill 1-2 seconds	Tachycardia < 20 above normal for age and/or Pale and/or Capillary refill 3 seconds	Tachycardia 20-29 above normal for age Gray and/or Capillary refill 4 seconds	Tachycardia ≥ 30 above or bradycardia ≥ 10 below normal for age or Gray Capillary refill ≥ 5 seconds
Respiratory	Within normal parameters No retractions	Respiratory rate > 10 above normal parameters using accessory muscles and/or 30+ %FiO ₂ or 3+ L/min	Respiratory rate > 20 above normal parameters and retractions and/or 40+ %FiO ₂ or 6+ L/min	Respiratory rate ≥ 5 below normal parameters with retractions and grunting and/or 50% FiO ₂ or 8+ L/min

